6. PLANNED ANALYSES

6.1. Subject Disposition

Subject disposition will be summarized with the number and percent of the following: geographic region, ITT population, per-protocol population, safety population, study treatment ongoing, discontinued treatment and reason, completed the study, discontinued the study and reasons for discontinuation.

6.2. Major Protocol Deviations

Subjects with major protocol deviations will be summarized by each category of deviations (see Section 6.6).

6.3. Demographics and Baseline Characteristics

All demographic and baseline characteristics will be summarized for the ITT population by treatment arm and all subjects combined.

Baseline clinical laboratory tests will be summarized for hematology and serum chemistry with NCI-CTCAE grade.

6.4. Prior and Concomitant Medications

Prior and concomitant medications will be coded to generic terms based on the World Health Organization (WHO) dictionary and will be summarized by Anatomical Therapeutic Chemical (ATC) class and drug generic term. Prior anticancer therapies include radiotherapy, surgery, chemotherapy, and systemic therapy.

6.5. Medical History

Number and percent of subjects who had abnormalities from their medical history will be summarized by System Organ Class (SOC), preferred terms (PT), and by treatment arm.

6.6. Extent of Exposure

Descriptive summaries include: total treatment duration in months, total number of cycles, total dose prescribed, total dose administered, dose intensity, relative dose intensity, and cycle delay. For the combination treatment arm, summaries will be provided for each study drug and for the combination as a whole.

Premedication for talacotuzumab will be summarized separately.

6.7. Efficacy

Unless specified otherwise, statistical inferences will be based on 2-sided p-values and 2-sided 95% confidence intervals (CI). For stratified analyses, subjects' strata recorded in the interactive web response system (IWRS) will be the data source.

6.7.1. Primary Efficacy Endpoints

6.7.1.1. Complete Response

Number and percent of subjects achieving CR will be presented by treatment arm. The odds ratio (decitabine + talacotuzumab vs. decitabine alone) will be reported along with the associated 95% CI based on a stratified logistic regression with treatment as the only covariate. The p-value will be based on a stratified Cochran-Mantel-Haenszel (CMH) test. Stratification factors are those used in randomization. Number of subjects achieving cytogenetic CR or molecular CR will be provided.

A sensitivity analyses will be performed using the per-protocol population.

Subgroup analysis will be performed and presented using a forest plot.

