Safety reviews will be performed in Part A and Part B. The safety assessments in Part A will occur prior to the initiation of Part B. This will include safety and available PK and PD data from single-agent talacotuzumab and the preliminary safety of the combination of decitabine + talacotuzumab. A Study Evaluation Team (SET) will monitor safety and study conduct on an ongoing basis during Part A of the study.

An Independent Data Monitoring Committee (IDMC) will be established to evaluate safety and efficacy data collected during Part B of the study as described in Section 3.1.

In addition to evaluations by investigators, disease status will be reviewed and determined by independent central review in a blinded fashion. Disease status based on independent central review will be the primary source for efficacy analyses.

After review of the data from Interim Analysis #2, the IDMC informed the Sponsor that the futility criterion for OS was met and that the CR rate did not meet per-protocol defined statistical significance. Given the lack of efficacy advantage of talacotuzumab + decitabine versus decitabine alone, the incidence of infusion-related reactions, and the complexities with premedications for drug administration, the benefit/ risk ratio is not favorable to continue treatment with talacotuzumab. The IDMC recommended closure of enrollment to the study and that subjects receiving talacotuzumab + decitabine should discontinue talacotuzumab treatment and may continue decitabine alone, according to Principal Investigator decision and subject agreement. All subjects will continue to be followed for survival and subsequent anti-cancer therapy. During the treatment phase with decitabine, subjects will be monitored for serious adverse events.

The end of study data collection is defined as when 270 deaths have occurred or 6 months after the last subject is enrolled, whichever occurs first. At that time, follow up of subjects will end. Subjects who are continuing to derive benefit from decitabine treatment as assessed by their investigator may continue to receive decitabine; during this period, only serious adverse events will be monitored and entered into the Company safety repository as described under Amendment 7.

SUBJECT POPULATION

Part A

Key eligibility criteria include the following: subjects diagnosed with AML according to the World Health Organization (WHO) 2008 classification system fulfilling all of the following criteria:

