11. STATISTICAL METHODS

Statistical analysis will be done by the sponsor or under the authority of the sponsor. A general description of the statistical methods to be used to analyze the efficacy and safety data is outlined below. Specific details will be provided in the Statistical Analysis Plan.

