- There will be a formal statistical testing for superiority for CR at the interim analysis of 80 subjects with 2-sided $\alpha=0.001$. The final analysis of CR (in terms of formal statistical hypothesis testing) will take place after 160 subjects have been randomized and followed for 4 months (to occur at the same time as the 1st interim analysis of OS) with 2-sided $\alpha=0.009$. The study and collection of response data continue after the final CR analysis regardless of the outcome of the analysis.
- Overall 2-sided $\alpha=0.04$ for OS; and if the final analysis of CR achieves statistical significance, then $\alpha=0.009$ allocated to this CR analysis can be reclaimed by OS analysis, ie, OS can be tested at the overall level of 0.049.
- The 2 interim analyses and final analysis for OS will utilize the O'Brien-Fleming α -spending procedure.

If the study stops enrollment after the first interim analysis, then the clinical cut-off will be when 90 EFS events have occurred. The analyses of these 120 subjects will be exploratory with EFS as the primary outcome of interest.

The overall statistical inference of the study can be summarized as in [Table 7](#).

Table 7: Overall Statistical Inference

Enrollment, No. of Subjects	Analysis	Clinical Cutoff	2-Sided α
40 subjects per arm	Interim analysis of CR and CR+CRi to determine enrollment continuation	4 months after 40 subjects per arm are randomized	0.001
Continue to approx. 400	CR final analysis	4 months after 160 subjects are randomized	0.009

OS interim analysis No.1	At the time of final CR analysis	0.0002
OS interim analysis No.2	180 deaths	0.0088/0.0116 ^a
OS final analysis	270 deaths	0.0372/0.0454 ^a
Stop with approx. 120 EFS final analysis ^b	90 EFS events	NA

^a If CR final analysis reaches statistical significance

^b Exploratory without formal statistical hypothesis testing

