11.4. Efficacy Analyses

Kaplan-Meier estimates of time to events, including OS and EFS will be presented, along with a stratified (by baseline ECOG performance status and type of AML) log-rank test comparing the 2 treatment arms. Median OS along with corresponding 95% confidence intervals (CIs) will be obtained from the Kaplan-Meier estimates. Cox's regression (stratified by baseline ECOG performance status and type of AML) will be applied to obtain the hazard ratio estimate and the corresponding 95% CI. Additional Cox's regression may be performed to include appropriate baseline prognostic variables.

Number and percent of subjects who have CR, CR+CRi, and CR plus MRD negative CRi will be calculated and compared between the 2 treatment arms using Fisher's exact test. Time to response and duration of response will also be summarized for subjects who have CR, CR+CRi, and CR plus MRD negative CRi.

Descriptive analysis will be performed for RFS.

Statistical analyses will be performed for all randomized subjects, as well as for subgroups defined by important baseline or disease characteristics, including CD123 status. Additional efficacy analyses may be performed to include appropriate data from Part A.

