- A second interim analysis will occur after 160 subjects (approximately 80 subjects per arm) have been randomized and followed for at least 4 months; this is the final analysis for CR rate and the first interim analysis for OS. The study will not be stopped on the basis of the CR rate results.
- A third interim analysis (ie, the second interim analysis of OS) will be conducted when 180 deaths have occurred.

- The final analysis of OS will take place when 270 deaths have occurred.

If the study stops enrollment after the first interim analysis based on the pre-specified criteria, it is expected that approximately 120 subjects will have been randomized. These subjects will continue to be followed. The clinical cutoff in this case will be when 90 EFS events have occurred.

Overall type I error of 0.05 (2-sided) will be allocated between the 2 primary endpoints CR rate and OS using a gate keeping procedure as described below:

- There will be a formal statistical testing for superiority for CR rate at the first interim analysis of 80 subjects with 2-sided $\alpha=0.001$. The final analysis of CR rate (in terms of formal statistical hypothesis testing) will take place after 160 subjects have been randomized and followed for at least 4 months (to occur at the same time as the 1st interim analysis of OS) with 2-sided $\alpha=0.009$. The study and collection of response data continue after the final CR analysis regardless of the outcome of the analysis.
- Overall 2-sided $\alpha=0.04$ for OS; if the final analysis of CR rate achieves statistical significance, then $\alpha=0.009$ allocated to this CR analysis can be reclaimed by the OS analysis, ie, OS can be tested at the overall level of 0.049.
- The 2 interim analyses and final analysis for OS will utilize the O'Brien-Fleming α -spending procedure.

Statistical inferences including efficacy stopping boundaries (in terms of nominal α -value) for all planned interim and final analyses (2 primary endpoints, CR rate and OS) are shown in Table 1.

Table 1: Overall Statistical Inference

Analysis	Description	Clinical Cutoff	2-Sided α
IA.1	CR and CR+CRi	4 months after 80 subjects (40/arm) are randomized	0.001
IA.2	CR final analysis	4 months after 160 subjects are randomized	0.009
	OS interim analysis No. 1		0.0002
IA.3	OS interim analysis No. 2	180 deaths	0.0088 / 0.0116 ^a
Final ^b	OS final analysis	270 deaths	0.0372 / 0.0454 ^a
^a If CR rate reaches statistical significance.			

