^b Final analysis will be carried out by Sponsor.			

An Independent Data Monitoring Committee (IDMC) will be established to evaluate safety and conduct the planned efficacy interim analyses. Upon completion of the first interim analysis, the IDMC requested a futility analysis of OS at the time of the second interim analysis. Survival data at the time of the second interim analysis will include approximately 100 deaths, which is 37% of the total 270 deaths planned at the final analysis. The futility boundary, in terms of the observed hazard ratio, is chosen to be 0.95. If the observed hazard ratio at the time of the secondary interim analysis is ≥ 0.95 , the OS result will be considered futile. Detailed characteristics of the futility criterion are described in a separate IDMC statistical analysis plan. This futility analysis was not pre-planned in the study protocol, hence is considered ad hoc.

The OS outcome met the futility criteria at the time of the second interim analysis; thereafter upon IDMC's recommendation, patient recruitment was terminated, treatment with talacotuzumab was discontinued, and treatment with decitabine may continue.

Analyses described in this document include all data from all randomized subjects up to the clinical cutoff that is defined as 6 months after the last subject was randomized.

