5.12. Interim Analyses

All interim analyses will be conducted by an external independent statistical group and reviewed by the IDMC. The IDMC procedures and interim analysis details are described in a separate IDMC charter and a statistical analysis plan, respectively.

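### Does it matter that the protocol names Fisher's exact test for complete response while the SAP uses a stratified CMH test?

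*SAP*

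**What the plan says.** Protocol section 11.4 states that the numbers with CR, CR+CRi and CR plus MRD-negative CRi "will be calculated and compared between the 2 treatment arms using Fisher's exact test". That test is unstratified. The same section stratifies the log-rank test and the Cox model by ECOG status and type of AML.

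The protocol introduces its statistics chapter (section 11) as a general description and adds: "Specific details will be provided in the Statistical Analysis Plan".

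For CR, SAP section 6.7.1.1 says: "The p-value will be based on a stratified Cochran-Mantel-Haenszel (CMH) test". The strata are the randomisation factors, and the odds ratio comes from a stratified logistic regression. SAP sections 6.7.2.2 and 6.7.2.3 apply similar analyses to the other two response rates.

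On timing, protocol section 11.2 says: "The final analysis of CR (in terms of formal statistical hypothesis testing) will take place after 160 subjects have been randomized". SAP section 3 repeats this: "The final analysis of CR rate (in terms of formal statistical hypothesis testing) will take place after 160 subjects have been randomized". Two-sided alpha is 0.009. The protocol (Synopsis and section 3.1) then records that "the CR rate did not meet per-protocol defined statistical significance" at the second interim analysis.

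The SAP's own analyses come later and "include all data from all randomized subjects up to the clinical cutoff that is defined as 6 months after the last subject was randomized". On interim methods, SAP section 5.12 says: "The IDMC procedures and interim analysis details are described in a separate IDMC charter and a statistical analysis plan, respectively".

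**The concern.** Two tests are named for one primary endpoint, and they can disagree near the boundary. The SAP shows that it can flag a departure, since section 3 labels the overall survival (OS) futility analysis ad hoc. It gives no such note for the CR test and does not say whether CMH is continuity-corrected. It also places a CR p-value under the heading for primary efficacy endpoints, at a cutoff after the CR alpha was spent, without calling it descriptive.

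At stake would be a CR p-value below 0.05 at the final cutoff, from a test the protocol does not name, being read as a positive primary result.

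**Working it through.** **Inputs.** CR rates of 40% vs 15%, 80% power, overall CR alpha 0.01 and 160 subjects (protocol Table 9, SAP Table 3). Alpha 0.009 at the 160-subject analysis (protocol Table 7, SAP Table 1). Allocation 1:1, so 80 per arm.

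**1. The plan's own figure.** With mean rate 0.275 and z-values 2.576 and 0.842, the uncorrected size per arm is

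n = [2.576·√(2·0.275·0.725) + 0.842·√(0.40·0.60 + 0.15·0.85)]² / 0.25² = 73.05, so 74.

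The continuity-corrected size is

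(73.05/4)·[1 + √(1 + 4/(73.05·0.25))]² = 80.9, so 81 per arm, 162 in total.

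The stated 160 therefore matches a Fisher-type calculation. Exact Fisher power at 80 per arm is 80.8% at alpha 0.01.

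**2. The tests at the formal analysis.** Every possible table at 80 per arm was enumerated with binomial weights, treating the trial as one stratum. With s responders in total and x in the combination arm, the Mantel-Haenszel (MH) statistic is (x − s/2)²/V, where V = 80²·s·(160 − s)/(160²·159). The corrected form subtracts 0.5 from |x − s/2| before squaring.

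| Test, alpha 0.009 | Power, 40% vs 15% | Size at 15% in both arms | Verdict differs from Fisher, 40% vs 15% |
|---|---|---|---|
| Fisher | 79.6% | 0.0047 | n/a |
| MH, uncorrected | 84.0% | 0.0083 | 4.4% |
| MH, corrected | 78.9% | 0.0040 | 0.7% |

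None exceeds 0.009. A four-stratum CMH simulation (36, 20, 16 and 8 per arm, assumed sizes) gave power of 83.9% to 84.9% and size of about 0.008, so the one-stratum figures are a fair guide.

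**3. Boundary examples.**

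- 27/80 vs 12/80: s = 39, V = 7.42, 7.5²/7.42 = 7.58. The p-value is 0.0059 uncorrected and 0.0094 by Fisher, so the two fall on either side of 0.009.
- 23/80 vs 12/80: s = 35, V = 6.88, 5.5²/6.88 = 4.40. The p-value is 0.0360 uncorrected, 0.0566 corrected and 0.0549 by Fisher, so they fall on either side of 0.05.

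The choice of test can therefore matter for a single result near a threshold.

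**4. The final cutoff.** The documents do not give the final number per arm, so 80 to 200 is assumed. The first 80 per arm are taken as the second-interim data and held fixed. With a true rate of 15% in both arms and a non-significant second interim, the chance of a later nominal p<0.05 is:

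| Test | Either direction | Favouring the combination |
|---|---|---|
| Fisher | 2.6% to 3.4% | 1.3% to 1.7% |
| MH, uncorrected | 4.0% to 4.6% | 2.0% to 2.3% |
| MH, corrected | 2.4% to 3.4% | 1.2% to 1.7% |

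Only the right-hand column matches the feared misreading. All its values lie below 2.5%, the one-sided share of a nominal 0.05. At a given size, moving from Fisher to uncorrected MH adds about 0.6 to 0.8 percentage points.

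**5. Status of the final-cutoff p-value.** Both documents make the 160-subject analysis the last formal CR test. The Final row of SAP Table 1 lists OS only. The 0.009 passes to OS only if that CR analysis succeeds, and the protocol records that it did not. Nothing computed under SAP section 6.7.1.1 can reopen either question.

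**The case for a change.** The strongest case for a change is that a named test is more than a detail. Once the protocol says Fisher, replacing it for a primary endpoint is a departure, and the sample size fits a Fisher-type calculation. The unstated continuity correction decides the 23/80 vs 12/80 example. If the true rates were 25% vs 15% (an assumption), the chance of a later nominal p<0.05 after a failed second interim would be 19% to 67% across tests and sizes. A short clarification would cost little.

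The undocumented difference stands, and it covers all three response rates. The rest carries less weight. The 19% to 67% is the chance of detecting an assumed true 10-point benefit; it is not an error rate. Its upper end needs the full 200 per arm, although enrolment closed early and SAP section 5.2 limits centrally reviewed endpoints to subjects with such a review or who died before one.

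The test behind the second-interim verdict cannot be seen here, because interim methods sit in a separate IDMC plan. That makes it unavailable to this review, not missing from the trial's plan. Adding Fisher beside CMH, or the word descriptive in section 6.7.1.1, would repeat what section 3 and Table 1 of the SAP already imply.

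**Conclusion.** No change is needed. An analyst following the SAP as written obtains a valid p-value from a test that matches the stratified randomisation and brings CR into line with the stratified OS analysis. Type I error is held at 0.009 in every version computed, the OS alpha is unaffected, and the reported second-interim CR verdict is not in question. What remains is an unrecorded substitution of test for three response rates, in a trial whose formal CR testing had already ended without significance.

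In size, the choice moves power by about 4 percentage points at the formal analysis (79.6% vs 84.0%). At the final cutoff, the chance of a nominally favourable CR p-value under no effect is about 1.2% to 2.3%. These figures rest on one stratum, a common CR rate of 15% for size and the null calculation, 80 to 200 per arm at the final cutoff, and second-interim response data that do not change afterwards. The last is a simplification, because both documents say response data continue to be collected after the final CR analysis. The conclusion does not depend on it, since the status of the later p-value follows from the text alone.

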6.7.1.2. Overall Survival

Overall survival (in months) is defined as the time from randomization to death from any cause. For subjects who are not known to have died, survival time will be censored at the date last known to be alive.

Number and percent of deaths will be provided. Kaplan-Meier estimates of the survival functions will be presented graphically. Median and 25th and 75th percentiles along with associated 95% CI will be provided. The p-value will be based on a stratified logrank test. The Hazard ratio (decitabine + talacotuzumab vs. decitabine alone) will be reported along with the associated 95% CI based on a stratified proportional hazard model with treatment as the only covariate. Stratification factors are those used in randomization.

Two sensitivity analyses will be performed: (1) analysis using the per-protocol population; and (2) analysis censored at the time of first curative-intent subsequent therapy.

Subgroup analysis will be performed and presented using forest plot.

6.7.2. Secondary and Exploratory Efficacy Endpoints

6.7.2.1. Event-Free Survival

Event-free survival (EFS) is defined as the time from randomization to treatment failure, relapse from CR or CRi, or death from any cause, whichever occurs first. Subjects who did not reach any of these events will be censored at the last tumor assessment.

EFS will be analyzed in the same fashion as that of overall survival.

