5.2. Subject Populations (Part B)

Intent-to-Treat (ITT): All subjects randomized into the study, grouped per treatment assigned by randomization, regardless of the actual treatment received. ITT will be used for summaries of disposition, demographics, baseline disease characteristics, and all efficacy analyses unless specified otherwise.

Upon early termination of study recruitment after the second interim analysis, subjects' disease status is no longer assessed by the IRC. For analyses of endpoints that depend on IRC assessment, only subjects in the ITT population who had IRC assessment will be included. Subjects who died before having data for IRC review will be included.

Per-Protocol (PP): Subjects in the ITT population who received at least 1 complete dose of decitabine for the decitabine alone arm and at least 1 complete dose of talacotuzumab for the decitabine + talacotuzumab arm and have no major protocol deviations in terms of study entry criteria that by clinical judgement will have a potential to impact efficacy outcomes (see Section 6.6). The per-protocol population will be used for sensitivity analyses of the primary efficacy endpoints CR rate and OS.

For analyses of endpoints that depend on IRC assessment, only subjects in the PP population who had IRC assessment will be included. Subjects who died before having data for IRC review will be included.

Safety: All randomized subjects who received at least one dose of study medication, grouped according to actual treatment received. This population will be used for all summaries of safety and study drug exposure.

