5.9. Disease Status per Central Review and Investigator’s Assessment

Disease status (including response) based on central review by the IRC will be the primary source for all pertinent analyses. Analyses based on investigator’s assessment will also be performed. Any major discordance between the 2 assessments affecting interpretation of study outcomes may be investigated.

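### IRC-based EFS counts deaths up to the final cutoff but censors event-free survivors back at their last assessment, so the median and especially the 75th percentile come out too low in both arms

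*SAP*

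**What the plan says.** SAP 6.7.2.1 defines EFS from randomisation to treatment failure, relapse from CR or CRi, or death from any cause. Its only censoring rule is "Subjects who did not reach any of these events will be censored at the last tumor assessment". It adds "EFS will be analyzed in the same fashion as that of overall survival", which brings in the Kaplan-Meier curve, the stratified log-rank test, the hazard ratio and, from SAP 6.7.1.2, "Median and 25th and 75th percentiles along with associated 95% CI will be provided".

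Three other passages bear on it:

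- SAP 5.9 makes central review the main source: "Disease status (including response) based on central review by the IRC will be the primary source for all pertinent analyses".
- SAP 5.2 says that after recruitment ended early, "disease status is no longer assessed by the IRC". Endpoints that depend on the IRC then keep only subjects with an IRC assessment, with one exception: "Subjects who died before having data for IRC review will be included".
- SAP 3 sets the data span as "all data from all randomized subjects up to the clinical cutoff that is defined as 6 months after the last subject was randomized".

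Neither document ends the counting of deaths for EFS at the date IRC review stopped.

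**The concern.** The last tumour assessment is read here as the last one reviewed by the IRC, because SAP 5.9 makes that the primary source. On this reading the end of a subject's time at risk depends on what happens next. Deaths are observed up to the cutoff through survival follow-up, while survival without an event is credited only up to the last IRC assessment. Among subjects past their last assessment, only those who will die remain in the risk set.

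That breaks the independent-censoring assumption of Kaplan-Meier estimation. At stake are the reported EFS curve and two of its three planned quartiles, in both arms.

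**Working it through.** **1. The plan's own EFS figure.** With HR 0.59, a 90% CI and 80% power (SAP 4), events = 4(1.645 + 0.842)² / (ln 0.59)² = 4 × 6.183 / 0.2784 = 88.8, so 89. Power with 90 events = Φ(√90/2 × 0.5276 − 1.645) = Φ(0.858) = 80.5%. The stated 90 events is reproduced.

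**2. The mechanism (illustrative dates).** Two subjects are event-free at an IRC assessment at month 4. IRC review stops at month 5 of their follow-up, and the cutoff falls at month 11. One dies at month 8 and is an event at 8. The other is alive at 11 and is censored at 4. From month 4 to 8 only the first is counted at risk.

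**3. Model inputs.**
- Control medians: assessed EFS 4.0 and OS 8.0 months (SAP 4). Monthly hazards that give these: failure or relapse 0.107, death before it 0.0781, death after it 0.1049.
- Combination arm at the planned effect: the first two hazards multiplied by 0.59.
- Marrow every 2 cycles from Cycle 2, Days 14-28 (Protocol Table 1B): first at Day 42-56, then every 56-63 days. Failure is dated at the visit that finds it.
- Accrual (assumed): 18 to 24 months. The planned rate of 120 in 15 months (Protocol 11.3) is 8 per month, so 160 subjects take 20 months, and 4 months of follow-up makes 24. SAP 3 says "Survival data at the time of the second interim analysis will include approximately 100 deaths"; the model gives 102 with 18 months of accrual and 113 with 24.
- Sample size = 160 × accrual/(accrual − 4): 160 × 18/14 = 206, or 160 × 24/20 = 192.
- Cutoff = end of accrual + 6 months. The gap from IRC stop to cutoff is not stated; 3 to 6 months is assumed.

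**4. Results for 18 months of accrual and a 6-month gap** (600,000 subjects per run; median / 75th percentile, months; repeat runs agree closely but not to the last digit):

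| Rule | Control | Combination |
|---|---|---|
| Reference: assessment continues to cutoff | 3.99 / 7.73 | 7.21 / 13.30 |
| SAP rule | 3.80 / 7.41 | 5.92 / 11.08 |
| Deaths after the stop removed, last-assessment censoring kept | 3.77 / 7.51 | 6.45 / 11.78 |
| Deaths after the stop kept, censoring at the stop date | 3.90 / 7.51 | 6.33 / 11.40 |
| One cut at the stop, censoring at the stop date | 4.00 / 7.73 | 7.21 / 13.29 |

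The combination reference median exceeds 6.8 because failures are dated at visits.

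The control median is 3.99 − 3.80 = 0.19 too low. Removing the late deaths leaves it 0.22 too low; changing only the censoring date leaves 0.09. Last-assessment censoring paired with counted deaths is therefore the main cause there. At the control 75th percentile (0.32 too low) either single change leaves 0.22, so both contribute. In the combination arm, removing late deaths takes the median shortfall from 1.29 to 0.76. The control 25th percentile is 1.77 against 1.78. About 16% of control EFS events are deaths after the stop.

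**5. Range over 18-24 months of accrual and a 3-6 month gap.** Control: median about 0.1-0.2 too low, 75th percentile about 0.2-0.3 (up to 0.5 if accrual of 15 months is included). Combination at the planned effect: about 0.5-1.3 and 1.2-2.2. For example, 24 months of accrual with a 6-month gap gives control 3.82 / 7.50 against 3.97 / 7.74; 18 months with a 3-month gap gives a combination median of 6.48 against 7.20.

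**6. Between-arm comparison.** Hazard ratio, reference against SAP rule: 1.000 and 0.999 at the null, 0.952 and 0.957 near 0.95, 0.592 and 0.618 at the planned effect. Rejection at the null under the SAP rule was 4.6% and 5.2% in two sets of simulated trials.

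**7. The SAP 5.2 restriction.** In the base case about 7 of 206 subjects without IRC data die and stay in, and about 10 are alive and dropped. A living subject with no assessment would otherwise be censored at randomisation and add nothing to the curve, so under the SAP rule dropping them moves no quartile.

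**The case against.** The strongest reply is that the effect is small and has no inferential consequence. With 103 subjects per arm, the standard error of an exponential median of 4 months is about 4 / (0.693 × √103) = 0.57 months, so a control shift of 0.19 is about a third of it. EFS is secondary and carries no alpha, and OS had already met the futility criterion at an observed hazard ratio of 0.95 or more. The large combination-arm figures therefore describe an effect the trial is unlikely to have had. All of this stands, and it is why the point is minor. It does not remove a one-directional error in planned outputs, which a confidence interval does not disclose.

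A second reply is that failures and relapses missed after the stop push the curve up. The simulation includes this; it reduces the bias but does not reverse it.

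A third is that investigator-assessed analyses are also planned. They are not a sure rescue: Protocol 9.1.4, 9.1.5 and 9.2.1 keep disease evaluations going, while Table 1C lists none.

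Some stronger readings are tempting but unsupported:

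- A reader might blame only the deaths after IRC review stopped. Removing them does not repair the control median.
- A reader might treat SAP 5.2's retention of the dead and exclusion of the living as a separate source of bias. It follows the same pattern but moves the quartiles little by itself.
- A reader might expect a control 75th percentile 0.5-1.6 months too low. That needs hazards giving an assessed EFS median of 4.74 and an OS median of 8.4, not the plan's 4.0 and 8.0.

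**Conclusion.** The point holds as a minor one. Under the SAP as written, the IRC-based EFS curve, its median and especially its 75th percentile are biased low in both arms, and more so the longer EFS is. The direction follows from the rules. The size rests on assumed accrual, an assumed gap between the IRC stop and the cutoff, exponential hazards, and the reading of the last assessment as an IRC one. SAP 5.2 also leaves open whether a screening IRC read counts as an IRC assessment; the bias remains if nobody is excluded.

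It would be wrong to infer that the treatment comparison is invalid. The hazard ratio is unbiased at the null and moves towards 1 under a true benefit, type I error is not inflated, and the CR and OS conclusions do not change.

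**What to change.** In SAP 6.7.2.1, for IRC-based EFS:

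- Set one data cut at the date IRC assessment stopped, and state that date.
- Count treatment failure, relapse and death only on or before it.
- Include all ITT subjects randomised by the cut, replacing the SAP 5.2 restriction for this endpoint. Keeping that restriction alongside stop-date censoring would leave the control median at 3.90 against 3.98.
- Censor event-free subjects still under scheduled assessment at the cut date, including those not yet assessed. Censor those whose assessments ended earlier at their last assessment.
- Keep the version that counts all deaths as a sensitivity analysis.

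For investigator-assessed EFS, first reconcile Protocol 9.1.4, 9.1.5 and 9.2.1 with Table 1C on whether local evaluations continued. Then apply the same kind of cut at the date that source ended.

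The cost is SAP wording and one derivation. EFS events fall from 167 to 141 in a simulated 206-subject trial (26/167 = 16%), and power at the planned effect falls from 83.6% to 82.5%. Some bias remains for subjects who stop assessments early and later die: if 8% do so, the control median and 75th percentile are 3.94 and 7.74 against 4.00 and 7.80.
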